3.4 Primary Safety Endpoints

This research study does not measure primary safety endpoints.

4 Subject Selection Enrollment and Withdrawal

4.1 Inclusion Criteria

Target accrual: 30 healthy adults will be recruited for this study.

Subject population: Healthy adults. Subjects will be able to provide written consent to be included in the research study. The inclusion criteria will be verified with the subjects and by review of the Mayo medical documents if available.

Inclusion Criteria:

- 1) Adults 18 years of age and older
- 2) Healthy subjects without known cardiovascular disease, thyroid disease or documented mental health illness
- 3) Subjects who are on no medications that have significant interaction with study drug.
- 4) Subjects with no prior history of regular amphetamine use, and non-prescription stimulants
- 5) Nonsmokers

4.2 Exclusion Criteria

Exclusion Criteria:

- 1) Subjects with known cardiovascular disease, thyroid disease
- 2) Subjects with history of psychotic disorders/mental health illness, including but not limited to anxiety, depression, bipolar disorder; history of substance abuse or dependence
- 3) Subjects currently taking medications that have significant interaction with study drug.
- 4) Prior history of regular amphetamine use, or non-prescription stimulants
- 5) Smokers
- 6) Pregnant subjects
- 7) Known lactose intolerance (due to presence of lactose in the prepared medication)
- 8) Family history of sudden cardiac death

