Stimulants such as amphetamines and methampethamies have been also increasing recognized to contribute to heat –related illness risk. Several case reports describing possible amphetamine related “heat stress” leading to complicated cardiovascular outcomes.¹²⁻¹⁵ Limited literature is currently available on the effects of stimulants on body’s core temperature and possible risk for stroke.

It is speculated that the adverse events are due to the high sympathomimetic action of stimulants. However, to our knowledge, the mechanisms and magnitude of such hemodynamic responses that may occur with nonmedical use of Adderall in Adderall-naïve, healthy young adults have not been studied in humans in a randomized, double-blind, placebo-controlled fashion.

The acute cardiovascular effects of stimulants in healthy young people are likely to be significant. Considering the increased use of Adderall in adults, these risks may be even higher in people with preexisting cardiac conditions (unidentified hypertension, coronary disease, silent arrhythmias) or in those with a family history of premature heart disease. The goal of the proposed clinical trial is to investigate acute cardiovascular effects of Adderall, administered orally, in healthy, young people not used to amphetamines. We hypothesize that taking an oral dose of Adderall, compared to a placebo pill, increases blood pressure (BP) and heart rate (HR) in Adderall-naïve healthy adults at rest and in response to conditions of mental and physical stress. Furthermore, we hypothesize that these hemodynamic changes are associated with sympathetic activation and

impaired endothelial and cardiac function, which could itself predispose to increased cardiovascular risk. Lastly, we hypothesize that taking an oral dose of Adderall, compared to a placebo pill, alters thermoregulation and acutely suppresses appetite in Adderall-naïve healthy adults.

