- Cardiovascular events: [U.S. Boxed Warning]: Use has been associated with serious cardiovascular events including sudden death in patients with preexisting structural cardiac abnormalities or other serious heart problems (sudden death in children and adolescents; sudden death, stroke and MI in adults). These products should be avoided in the patients with known serious structural cardiac abnormalities, cardiomyopathy, serious heart rhythm abnormalities, or other serious cardiac problems that could increase the risk of sudden death that these conditions alone carry. Patients should be carefully evaluated for cardiac disease prior to initiation of therapy. Patients who develop symptoms such as exertional chest pain, unexplained syncope, or other symptoms suggestive of cardiac disease during treatment should undergo a prompt cardiac evaluation.
- CNS effects: Amphetamines may impair the ability to engage in potentially hazardous activities.
- Peripheral vasculopathy: Stimulants are associated with peripheral vasculopathy, including Raynaud's phenomenon; signs/symptoms are usually mild and intermittent, and generally improve with dose reduction or discontinuation. Digital ulceration and/or soft tissue breakdown have been observed rarely; monitor for digital changes during therapy and seek further evaluation (eg, rheumatology) if necessary.
- Visual disturbance: Difficulty in accommodation and blurred vision has been reported with the use of stimulants.

Disease-related concerns:

- Abuse potential: [U.S. Boxed Warning]: Potential for drug dependency exists; prolonged use may lead to drug dependency. Use is contraindicated in patients with history of drug abuse.

Prescriptions should be written for the smallest quantity consistent with good patient care to minimize possibility of overdose.

- Hypertension: Use with caution in patients with hypertension and other cardiovascular conditions that might be exacerbated by increases in BP and HR. Use is contraindicated in patients with moderate to severe hypertension.

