7.3 Subject Population(s) for Analysis

All-randomized population: Any subject randomized into the study.

8 Safety and Adverse Events

The overall study risk for this protocol is considered greater than minimal risk.

Consent: Consent will be obtained before initiating study specific procedures. A quiet, comfortable, and private setting for the informed consent process will be provided. The consent process will be explained to the subject, time will be provided to consider all options and when possible the subject will be provided a copy of the consent form well in advance for review at

home. Study staff will consider the subject's likely reading abilities and provide an impartial witness in the informed consent process if necessary. All questions will be answered. Coercion or other undue influences will be avoided through the use of a quiet, comfortable, and private setting away from areas involved in direct clinical practice will be used for the informed consent process. The subject will be told that informed consent can be revisited at any time and consent can be withdrawn at any time without affecting the subject's medical care. The informed consent process will continue throughout the subject's participation in the study and consent will be informally verified on a continuing basis. Significant new information will be given to the subject as it is available.

Safety: While the measurements and interventions proposed in these studies are used frequently and often on a routine basis in our laboratory, there are some risks to some of the measurements and interventions which will be described below:

- The major risk is that of possible side effects of Adderall. The side effects are outlined in the prior sections of this document. As with any medication, allergic reactions are also a possibility. We will enroll only healthy young subjects. This risk potentially induced by Adderall will be minimized by administering short acting form of Adderall and only one time dose. In the event that subjects develop sustained side effects such as elevated BP, elevated HR or other form of arrhythmia that may acutely compromised subject's health, emergent care will be provided by the medical staff.
- To control for behavioral risks, subjects with a history of psychiatric disorders will be excluded from participation.

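### Blood pressure and an ECG are recorded before the pill on both days, but no step in the supplied protocol makes dosing depend on them, so undetected moderate to severe hypertension is left to judgement without a threshold

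*Combined protocol and SAP*

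**What the plan says.** **Eligibility.** Section 4.1 asks for healthy adults without known cardiovascular disease. The cardiac exclusions in Section 4.2 are "Subjects with known cardiovascular disease, thyroid disease" (item 1) and sudden cardiac death in the family (item 8). Section 4.1 adds: "The inclusion criteria will be verified with the subjects and by review of the Mayo medical documents if available". Hypertension is not named in either section, and neither gives a BP, HR or ECG value.

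**Visit steps.** On Day 1 (Section 6.1), supine BP/HR, ECG, paced breathing, the baseline endothelial function test and orthostatic BP/HR are steps 9 to 13, and the capsule is step 14. On Day 2 (Section 6.2) the same measurements are steps 7 to 11, and the capsule is step 12. The only result that a numbered step ties to not dosing is a positive pregnancy test (Day 1 step 5, Day 2 step 4).

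**Drug information.** Section 1.4 reproduces published prescribing text: "Use is contraindicated in patients with moderate to severe hypertension" and "Patients should be carefully evaluated for cardiac disease prior to initiation of therapy". Section 1.1 itself says that risk may be higher where hypertension is unidentified or an arrhythmia is silent.

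**General safeguards.** The principal investigator may end participation in the subject's interest (Section 4.4.1) and is responsible for overseeing safety (Section 8.5). The stopping rules (Sections 8 and 8.4) apply when an exclusion criterion is met during participation or a significant safety concern arises.

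**The concern.** An exclusion limited to known disease cannot remove disease that nobody has yet found. Subjects are recruited by word of mouth or from a list of earlier research volunteers (Section 4.3), so records may be thin. The first objective look at BP may be the baseline recording itself, and the written sequence runs from that recording to the capsule without a decision point.

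What is at stake is subject safety. Section 8 rates the study as greater than minimal risk, and these volunteers have no clinical indication for the drug. They receive 25 mg in one dose, and Section 1.2 allows 35 mg if the run-in finds 25 mg inadequate. Handgrip, mental arithmetic and cold pressor tests follow the measurements that start three hours after dosing, which is the stated time of peak effect. The readings needed to keep a contraindicated subject away from this are already being collected.

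**Working it through.** The point rests on the text. No figure in the plan is in dispute.

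**1. Is there a measured cardiac criterion?** Sections 4.1 and 4.2 contain none. Section 4.3 has staff apply the inclusion criteria from available medical records. Day 1 step 6 and the medical history interview collect what the subject can report. Neither turns a reading into a criterion.

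**2. Are the readings available before the capsule?** Yes, on both days, as listed above. Paced breathing uses continuous finger BP. The ultrasound item in the study descriptions after Section 6.2 sets the forearm cuff 50 mmHg above SBP, up to 200 mmHg, so the team needs the current SBP.

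**3. Does any reading decide dosing?** Read in order, steps 9 to 13 and then 14 (Day 1) and steps 7 to 11 and then 12 (Day 2) contain no limit, no comparison and no instruction to withhold.

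**4. What standard do the documents offer?** For BP, the reproduced contraindication is not confined to diagnosed cases. For rhythm the text is weaker: the advice to avoid use concerns "known serious structural cardiac abnormalities, cardiomyopathy, serious heart rhythm abnormalities", that is, recognised disease. The ECG part therefore rests on the general advice to evaluate before therapy and on the background remark in Section 1.1.

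**5. What would stop a contraindicated subject?** Only Sections 4.4.1, 8, 8.4 and 8.5. None names a value.

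**6. Exposure.** 30 subjects × 2 capsules = 60 dosings, 30 of them active.

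**7. Illustration of size (prevalences assumed, not from the documents).** If a fraction p of recruits had undetected moderate to severe hypertension, the chance of at least one among 30 is 1 − (1 − p)^30, and the number to screen for 30 eligible is 30/(1 − p), rounded up.

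| Assumed p | At least one of 30 | Number to screen |
|---|---|---|
| 0.5% | 14% | 31 |
| 1% | 26% | 31 |
| 2% | 45% | 31 |
| 5% | 79% | 32 |

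The table shows only that the answer depends on p, and that screening losses would be small across this range.

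**8. Effect of the fix on power.** Section 7.1 gives a 4% difference and an SD of 5%, with two-sided alpha 0.05, and states 80% power. That figure is not at issue here; two independent groups of 25 give about 79% by the t test. For the crossover I used a paired t test (noncentral t) and supposed, as an assumption, that 3 of 30 second periods were lost and not replaced.

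- If 5% is the SD of each change and the two days are uncorrelated: d = 4/(5√2) = 0.566. Power is 85% with 30 pairs and 81% with 27.
- If 5% is the SD of the paired difference: d = 4/5 = 0.80. Power is 99% with 30 pairs and 98% with 27.

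**The case against.** The strongest reply is that the protocol is not blind to these readings. The investigator may withdraw anyone, must oversee safety and works under a stopping rule. A clearly severe baseline could be treated as cardiovascular disease that is now known, and stopped. Subjects must be healthy, give a history and complete a cardiovascular data sheet. All this stands, and a dramatic reading would probably be acted on. What it does not supply is a value, so a moderately raised reading, which can already fall within the contraindication, is left open.

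A reader might infer that nobody need look at BP before dosing. The documents do not support that, because the cuff setting requires SBP. It is a test setting, however, not a clearance. The only consequence written there for a high value is that cuff pressure is capped, which takes effect from an SBP of 200 − 50 = 150 mmHg.

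A reader might also infer that later monitoring is too short. Section 8.1 keeps subjects under observation until the day's protocol is complete and sends them to the Emergency Department for side effects in the following 24 hours, so the point does not lean on observation time. Nor does it lean on the open-ended age criterion ("Adults 18 years of age and older"), which is a separate eligibility matter.

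There are real mitigations: one short-acting dose, 25 mg against a cited usual daily maximum of 40 mg for adult ADHD, BP every 1 to 3 minutes, continuous ECG and medical staff at hand. They limit harm after the capsule is swallowed. They do not decide who should swallow it.

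Finally, the Data and Safety Monitoring Plan (Section 10.1), the separate IRB Protocol cited in Section 6, the data sheet and the flowchart were not supplied. A hold rule may exist there.

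**Conclusion.** The point holds for the supplied protocol and should be fixed before enrolment. Following the written steps, a volunteer with undetected moderate to severe hypertension can be dosed unless someone chooses to intervene. The BP part is firm. The ECG part is secondary and precautionary, because the reproduced advice on rhythm concerns recognised abnormalities.

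The size is 60 dosings without a written go/no-go rule, 30 of them active. The number of subjects who would be stopped is unknown, and the table in the working is conditional on assumed prevalences. Two stronger conclusions are not available: that the plan has no protection at all, since discretionary rules exist, and that no hold rule exists anywhere, since several attachments were not seen. The prescribing text in Section 1.4 is reproduced information, not a trial rule. The point is that the protocol does not turn it into one. Confidence is moderate, mainly because of those unseen attachments.

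**What to change.** 1. Add to Section 4.2 an exclusion for a pre-dose resting BP at or above a numeric limit, confirmed on repeat. Fix the limit in the protocol before enrolment, no higher than the lower bound of moderate hypertension.
2. Add a go/no-go line before step 14 of Section 6.1 and before step 12 of Section 6.2. The investigator, or a qualified team member already present, checks the recorded BP/HR against the limit and looks at the baseline ECG for an obvious serious rhythm abnormality. The capsule is withheld if either is found.
3. If the Data and Safety Monitoring Plan or the IRB Protocol already holds such a rule, cite it at these two steps instead.
4. Optionally, state how a randomized but undosed subject is counted in the all-randomized population (Section 7.3).

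**Cost.** One amendment and 60 brief checks. At an assumed 5 to 10 minutes each, 60 × 5 = 300 minutes and 60 × 10 = 600 minutes, or 5 to 10 hours over the whole trial. Occasional Day 1 screen failures are absorbed because enrolment continues until the target number complete (Section 4.4.1). A subject held on Day 2 loses the second period, and Section 7.2 allows single-day data to be analysed. Because the hold depends on a recorded pre-dose value and staff are blinded, the ignorable-missingness assumption stays plausible if that value is kept in the model. Under the loss assumed above, power stays at 81% or more. Pharmacy must reconcile any withheld capsule (Section 5.9.4).

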Central nervous system: Insomnia (extended release: 12% to 27%), headache (extended release; adults: $\leq 26\%$), emotional lability (extended release: 2% to 9%), anxiety (extended release; adults: 8%), agitation (extended release; adults: $\leq 8\%$), dizziness (extended release: 2% to 7%), nervousness (extended release: 6%), drowsiness (extended release: 2% to 4%), speech disturbance (extended release: 2% to 4%), twitching (extended release: 2% to 4%), aggressive behavior, depression, dysphoria, euphoria, exacerbation of vocal tics, formication, irritability, outbursts of anger, overstimulation, paresthesia, psychosis, restlessness, talkativeness

Dermatologic: Diaphoresis (extended release: 2% to 4%), skin photosensitivity (extended release: 2% to 4%), alopecia, dermatillomania, skin rash, urticaria

Endocrine & metabolic: Weight loss (extended release: 4% to 10%), decreased libido (extended release: 2% to 4%), dysmenorrhea (extended release: 2% to 4%)

Gastrointestinal: Decreased appetite (extended release: 22% to 36%), xerostomia (extended release: 2% to 35%), abdominal pain (extended release: 11% to 14%), nausea (extended release: 2% to 8%), vomiting (extended release: 2% to 7%), diarrhea (extended release: 2% to 6%), constipation (extended release: 2% to 4%), dyspepsia (extended release: 2% to 4%), teeth clenching (extended release: $\leq 4\%$), tooth infection (extended release: $\leq 4\%$), anorexia (extended release: 2%), bruxism, unpleasant taste

Genitourinary: Urinary tract infection (extended release: 5%), impotence (extended release: 2% to 4%), frequent erections, prolonged erections

Hypersensitivity: Anaphylaxis, angioedema, hypersensitivity reaction

Infection: Infection (extended release: 2% to 4%)

Neuromuscular & skeletal: Dyskinesia, rhabdomyolysis, tremor

Ophthalmic: Blurred vision, mydriasis

Respiratory: Dyspnea (extended release: 2% to 4%)

Miscellaneous: Fever (extended release: 5%)

<1% (Limited to important or life-threatening): Cardiomyopathy, cerebrovascular accident, Gilles de la Tourette's syndrome (exacerbation), peripheral vascular disease, seizure, toxic epidermal necrolysis

Warnings/Precautions:

Concerns related to adverse effects:

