- Psychiatric disorders: Use with caution in patients with preexisting psychosis or bipolar disorder (may induce mixed/manic episode). May exacerbate symptoms of behavior and thought disorder in psychotic patients; new onset psychosis or mania may occur with stimulant use; observe for symptoms of aggression and/or hostility. Screen patients with comorbid depressive symptoms prior to initiating treatment to determine if they are at risk for bipolar disorder.
- Seizure disorder: Limited information exists regarding amphetamine use in seizure disorder (Cortese, 2013). The manufacturer recommends use with caution in patients with a history of seizure disorder; may lower seizure threshold leading to new onset or breakthrough seizure activity.
- Tourette syndrome: Use with caution in patients with Tourette syndrome; stimulants may unmask tics.

To minimize the risk of side effects, we elected to use a short acting form of Adderall. Participants will be closely monitored in the CRTU at St Mary's Hospital where medical personnel is available to assist if medical needs were to arise.

2 Study Objectives

Primary Objective

- 1) Determine the hemodynamic changes (magnitude of BP and HR response) in healthy adults after taking one dose of prescription medication Adderall 25 mg orally, one time, and compare these responses to those after a placebo pill

Secondary Objective

- 1) Determine ECG changes and incidence of arrhythmias after consumption of Adderall compared to baseline ECG
- 2) Determine if consumption of a dose of Adderall is associated with altered neurohormonal and cardiovascular activation, assessed by measurements of biomarkers, such as catecholamines before and after Adderall/placebo intake
- 3) Determine if taking Adderall induces orthostatic changes
- 4) Assess baroreflex sensitivity (pace breathing) after Adderall vs placebo intake
- 5) Determine the effect of Adderall on cardiovascular hemodynamics during stress conditions including mental stress (arrhythmics), physical stress (sustained hand grip) and pain stress (cold pressor stress) as compared to measurements at rest
- 6) Determine the changes in heart function and brachial artery reactivity after Adderall intake by using an ultrasound
- 7) Determine the changes in appetite and food consumption after Adderall vs placebo

- 8) Determine the prevalence of stimulant medication use, history of weight changes and dietary habits among healthy adults (utilizing standard questionnaires)

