4.3 Subject Recruitment, Enrollment and Screening

Study personnel will recruit subjects by word-of-mouth. Study personnel will review whether the subjects meet the inclusion criteria (Section 4.1 of this document), based on review of their available medical records.

Dr. [REDACTED]' lab also keeps a list of prior research participants who were recruited as healthy adults for other research studies and who agreed to be contacted for future studies. Study personnel will review this list and if subjects fulfill the inclusion criteria they will be contacted via the phone, to consider participation in the study (see the attachment: Verbal and Phone Recruitment Script).

Eligible subjects will be thus approached by the study personnel and study will be explained in detail. If subjects show interest in participation, their contact information will be collected and forwarded to study team/study coordinator.

Subjects will sign IRB approved consent form when presenting to the CRTU for the research study. Informed consent may also be obtained via Ptrax digital signature capture technology on Mayo devices.

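### Section 4.2 does not name a history of seizure disorder as an exclusion, so a past, untreated seizure disorder is not clearly barred from dosing

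*Combined protocol and SAP*

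**What the plan says.** Section 1.4 carries two statements about seizure. Among the disease-related concerns it repeats the manufacturer's advice: "use with caution in patients with a history of seizure disorder; may lower seizure threshold leading to new onset or breakthrough seizure activity". In the adverse-reaction list, the group of important or life-threatening reactions below 1% ends with "exacerbation), peripheral vascular disease, seizure, toxic epidermal necrolysis".

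Section 4.1 has five inclusion criteria. The one that bears on general health reads "Healthy subjects without known cardiovascular disease, thyroid disease or documented mental health illness". The section adds: "The inclusion criteria will be verified with the subjects and by review of the Mayo medical documents if available".

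Section 4.2 has eight exclusion criteria: cardiovascular or thyroid disease; mental health illness or substance abuse; interacting medication ("Subjects currently taking medications that have significant interaction with study drug"); regular amphetamine or non-prescription stimulant use; smoking; pregnancy; lactose intolerance; and a family history of sudden cardiac death. No seizure or other neurological condition is named.

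Section 4.3 describes screening: "Study personnel will review whether the subjects meet the inclusion criteria (Section 4.1 of this document), based on review of their available medical records". The medical history interview is described among the study procedures at the end of section 6.2. Section 8 says that only healthy young subjects will be enrolled, and that "subjects with a history of psychiatric disorders will be excluded from participation".

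**The concern.** The Introduction states that the drug is not clinically indicated in these subjects. No treatment benefit therefore offsets a risk that the protocol itself describes, and the normal response is to keep people at raised risk out of the study.

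The usual way to act on a prescribing caution is to start low and titrate. This study does neither. Section 1.4 gives an adult starting dose of 5 mg once or twice daily in ADHD and 10 mg daily in narcolepsy, each raised weekly. The study gives 25 mg at once to people without regular amphetamine use, and section 1.2 allows an increase to 35 mg. With the dose fixed, eligibility is the main control left before dosing.

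At stake is whether a volunteer who discloses a past seizure disorder is dosed. As written, that depends on how staff read the word *healthy*, on the day of the visit.

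**Working it through.** No arithmetic settles this point, and the plan gives no figure to reproduce. The check is a reading of every eligibility criterion and every mention of seizure.

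**1. Count of criteria.** 5 inclusion (section 4.1) + 8 exclusion (section 4.2) = 13. Criteria naming seizure, epilepsy or any neurological disorder: 0 of 13. Seizure appears only in section 1.4; section 8 adds no seizure-related screening rule.

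**2. Which criteria could reach a past, untreated seizure disorder?**
- Exclusion 1 covers cardiovascular and thyroid disease. It does not reach it.
- Exclusion 2 covers mental health illness and substance abuse. Its list is open-ended, but within mental health.
- Exclusion 3 covers current interacting medication. It might remove someone on treatment, but not someone off treatment.
- Exclusions 4 to 8 are unrelated.
- Inclusion 2 opens with the word *healthy*. This is the only criterion that can reach it, and the conditions it spells out are cardiovascular, thyroid and mental health.

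**3. Comparison with the other cautions.** Section 1.4 lists five disease-related concerns. Drug abuse and psychiatric disorders are named in exclusion 2. Hypertension can be read into cardiovascular disease, and Tourette syndrome into the open-ended mental health wording. Seizure disorder can be read only into *healthy*. The psychiatric caution is worded much like the seizure caution, "Use with caution in patients with preexisting psychosis or bipolar disorder", and psychiatric history is nevertheless a named exclusion.

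**4. Dose against the section 1.4 starting doses.** 25 / 5 = 5 times a single adult ADHD starting dose; 25 / 10 = 2.5 times the narcolepsy starting dose. At 35 mg the ratios are 35 / 5 = 7 and 35 / 10 = 3.5.

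**5. Timing.** In section 6.1, consent is step 3, the Cardiovascular Research Data Sheet is step 6 and dosing is step 14, all on one day. A question asked before dosing fits the existing order. The data sheet is not in the documents, so it cannot be said whether it already asks about seizures. If it does, no rule in section 4.2 is attached to the answer.

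**6. Later safeguards.** The stopping rules (sections 8 and 8.4) include meeting an exclusion criterion during the study. With seizure history unnamed, a disclosure between the two visits would not trigger that limb; only the general limb on significant safety concerns would remain.

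**The case against.** The strongest reply is that the plan already has a binding rule. Inclusion 2 can be read as healthy *and* without the listed conditions. A known seizure disorder would then fail an inclusion criterion, and section 8 repeats that only healthy young subjects are enrolled. Section 4.1 requires verification with the subject as well as from records. The medical history interview covers past and present history. Under section 4.4.1 the principal investigator may end participation in the subject's interest, and dosing takes place in a clinical unit with medical staff at hand. The source is also soft: section 1.4 says that information is limited and advises caution, while the same list uses the word contraindicated for drug abuse and for moderate to severe hypertension. Exposure to the drug is a single short-acting dose.

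Much of this stands. A reader might infer that nothing in the plan stops such a volunteer from being dosed. The documents do not support that, because the healthy-subject requirement can fairly be read to bar them. A reader might also infer that the sponsor worked through the label cautions one by one and missed this one. That is not shown either: section 8 gives control of behavioral risks as the reason for the psychiatric exclusion.

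What the reply does not do is make the rule clear. The reading that bars the volunteer is one of two that the sentence allows. The discretionary safeguards do not set eligibility. The softness of the caution is no reason to leave it out, since the psychiatric caution is similarly worded and has a named exclusion.

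**Conclusion.** The point holds in a limited form. A past, untreated seizure disorder is not clearly barred by sections 4.1 and 4.2, although section 1.4 describes the risk and the subjects have nothing to gain from the drug. The existing safeguards make dosing such a volunteer unlikely, so this is a change that should be made rather than a fault that undermines the trial.

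The size cannot be quantified. The documents give no frequency of seizure history among volunteers and no seizure risk after a single dose; the below-1% heading in the reaction list supplies neither. Any number of expected cases would be an assumption and would say nothing about harm.

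The conclusion rests on the visible text. The data sheet, the recruitment script and the IRB attachments were not available and may already ask about seizures. Sample size, endpoints and analysis are unaffected.

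**What to change.** Add a history of seizure disorder to the exclusion list in section 4.2, and have staff confirm it at the visit-1 medical history interview before the capsule is given. Once it is listed, the stopping rule on exclusion criteria also covers a disclosure made after visit 1.

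The cost is a few words in a protocol amendment and at most one added question, or none if the Cardiovascular Research Data Sheet already asks it. The downside is the possible loss of a rare volunteer who would otherwise have qualified.

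Optionally, the same amendment could let the record review in section 4.3 refer to section 4.2 as well as section 4.1. The main fix does not depend on it.
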